10.1 Schedule of Events

10.1.1 Screening Visit (Visit 1)

A screening visit will be performed within 30 days prior to the scheduled procedure and may be

Medtronic Business Restricted

This document is electronically controlled

CONFIDENTIAL 056-F275 Rev E Clinical Investigation Plan Template

combined with the surgical procedure visit. Subjects will be consented before any procedures specific to the study are undertaken. If the subject is consented prior to the day of surgery, a re-verification of eligibility will be signed off by the PI or Sub-I on the day of surgery. The purpose and all aspects of the study will be explained to the subject. Subjects who agree to study participation must sign and personally date an IRB-approved informed consent form prior to participating in any study activities.

Once informed consent has been obtained according to IRB requirements and eligibility is confirmed, the subject's demographics and medical history will be assessed. Relevant medical and surgical history will be assessed and included in the electronic case report form (eCRF).

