12.1 Adverse Events

All Adverse Events (AEs) will be collected, starting from the time the informed consent form is signed through 30 days (+7) after the day of the procedure regardless of their severity or relationship to the Hugo™ RAS or study procedures. After 30 days, AEs will be assessed by the surgeon and those AEs deemed attributable to the underlying surgical indication, procedure or surgical device will be reported. All deaths will be collected via AE regardless of relatedness. Reporting of these events to Medtronic will occur on an AE Form, including event description, date of AE, treatment, resolution, assessment of both the seriousness of the AE and the relatedness to the system components. Each AE must be recorded on a separate AE eCRF.

AE definitions used in this study are based on ISO 14155:2020 (Clinical Investigation of Medical Devices for Human Subjects -- Good Clinical Practice). Documented pre-existing conditions are not considered AEs unless the nature or severity of the condition has worsened. See **Section 14.1** for details regarding AE analyses in each study analysis set. In addition, AEs impacting users or other persons (non-subject AEs) will be collected on a non-subject AE CRF.

Any unresolved procedural or device-related events that are still ongoing past study exit will be monitored by the physician per their institutional standard-of-care.

Unavoidable adverse events (UAE) (those that are inherent to the procedure and are expected to occur in all subjects for an expected duration) listed in **Table 9** will not be captured or reported unless the adverse event worsens or persists outside the stated timeframe post procedure. **Section 11.1** includes a list of several, but not an all-encompassing anticipated adverse events.

All deaths, serious adverse events related to the Hugo™ RAS System and/or study procedures and Clavien-Dindo Grade III and IV complications will be adjudicated by an independent CEC.

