14.4.2 Primary Objective #2 (Safety)

The primary safety objective of this study is to confirm that the Medtronic Hugo™ RAS System is safe when used for urologic robotic assisted surgery. The primary safety endpoint is the rate of subjects with major complications (meeting Grade III criteria or higher per the Clavien-Dindo Classification system) from the first incision through 30 days post-procedure. Further details can be found in **Section 6.4.2**.

The primary safety hypothesis is to test the overall 30-day major complication rate (i.e., rate of subjects with one or more major complications) against a performance goal. Since the safety profiles or major complication rates are very different among the three surgeries, a separate performance goal is pre-specified for each of the three surgery types (as per FDA recommendation). The performance goals are determined based on published literature data.

Let R be the 30-day major complication rate, and PG be performance goal for a specific surgery group. The statistical hypothesis is formulated as follows:

$$H_0: R \geq PG \text{ vs. } H_a: R < PG$$

The hypothesis will be tested using the Clopper-Pearson exact method and the null hypothesis will be rejected if one-sided p-value is significant comparing to alpha determined after multiplicity adjustment as described in **Section 14.12**.

Performance Goal Rationale and Sample Size

The literature search was performed based on available literature for each of the three surgery types (nephrectomy, prostatectomy, cystectomy). Point estimates along with 95% and 99% predicted intervals were calculated to provide plausible range of potential effect sizes. Clinically meaningful margins and statistical precisions have been taken into account to determine the appropriate performance goals. In some situations, considerations were also given to align with the studies from comparable sample sizes. The calculation details and rationales are summarized in the following table.

All sample size calculations are based on exact test. Presuming a one-sample proportion and one-sided test with the least alpha of 0.008 (0.025/3) when performing three hypothesis testing (nephrectomy, prostatectomy, and cystectomy, respectively) and adjusting for multiplicity in primary safety objectives, sample size justification and performance goals are described as below:

Surgery Type	Performance Goal (PG)	Sample Size	Rationale

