4.1.2 Primary Safety Objective

The primary safety objective of this study is to confirm that the Medtronic Hugo™ RAS System is safe when used for urologic robotic assisted surgery. The primary safety endpoint is the rate of subjects with major complications from the first incision through 30 days post-procedure. A major complication is defined as Grade III or higher complication per the Clavien-Dindo Classification system.

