7.9.2.2 Endpoint Definition and Derivation

Rate of major complications within 30 days is calculated as the proportion of subjects who experience an AE with Grade III Clavien-Dindo classification or higher that is related to any of device, procedure, or underlying condition/disease prior to or during the 30 calendar-days post-procedure. The procedure date, AE start date, CEC-adjudicated relatedness (device, procedure, underlying condition/disease) and Clavien-Dindo Classification collected with the adverse event will be used to determine whether a related major complication was experienced within 30 days. The proportion of subjects experiencing a major complication must meet a performance goal based on the indication for surgery.

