7.9.3.1 Objectives, Endpoint Definitions and Derivations

Endpoint #	Objective	Endpoint Definition and Derivation
1	Overall Complication Rate	Rate of overall complications within 30 days is calculated as the proportion of subjects who experience any related (device, procedure, or underlying condition/disease) adverse event prior to or during the 30 calendar-days post-procedure. The AE start date collected with the adverse event will be used to determine whether a complication was experienced.
2	Operative Time	Operative time is defined as the difference in time in minutes between the procedure end time and the procedure start time. The procedure start time is the time of first incision and the end time is the time of skin closure.
3	Intraoperative Estimated Blood Loss	The estimated amount of blood loss is reported during the procedure in mL.
4	Transfusion Rate	Occurrence of a blood transfusion is captured as an adverse event. A blood transfusion is defined as an AE that resulted in any treatment and then a bleeding complication led to a blood transfusion and started prior to or during the 30 calendar-days post-procedure.
5	Device-related Conversion	A conversion is defined the same way as in Section 7.9.1.2 . A device related conversion is defined as a conversion where either the primary or any other reason for conversion is denoted as Adverse Event that is related to the device or procedure, Device Deficiency, Non-Subject Adverse Event, or Poor Visualization.

6	Hospital Length of Stay	
The length of hospital stay is the number of days that the subject was in the hospital from the start of the surgical procedure to hospital discharge. The number of days in the hospital can be found as the difference in minutes between the discharge date and time and the procedure date and time divided by 1440 min/hour, i.e.,
 $(Discharge Date and time - procedure date and time)/1440.$
7	Readmission Rate	A readmission in a subject is identified if a related (device, procedure, or underlying condition/disease) adverse event with a start date of or after the index procedure date and prior to or during the 30-calendar days post-procedure that resulted in the subject being hospitalized. Additionally, the hospital start date reported within the AE must be prior to or during the 30 calendar-days post-procedure and on or after the reported index procedure discharge date.

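### The SAP's derivation of the primary safety endpoint has an upper time limit but no start, which conflicts with the SAP's own definition and the protocol's, both of which start at first incision

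*SAP*

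**What the plan says.** The endpoint definition is consistent across both documents. Protocol 14.4.2 takes the rate of subjects with major complications "from the first incision through 30 days post-procedure". SAP 4.1.2 has the "rate of subjects with major complications from the first incision through 30 days post-procedure", and SAP 7.9.2 repeats this directly above the derivation. Protocol 10.6 also limits the analysis of adverse events in the full analysis set (FAS) to first incision onward.

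The derivation in SAP 7.9.2.2 is worded differently. It counts Grade III or higher events related to device, procedure or underlying disease that occur "prior to or during the 30 calendar-days post-procedure". Its listed inputs are "The procedure date, AE start date, CEC-adjudicated relatedness (device, procedure, underlying condition/disease) and Clavien-Dindo Classification collected with the adverse event". No start point is written, and neither incision time nor event time is an input.

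The data to which the derivation applies begin earlier. Under protocol 12.1, adverse events are collected "starting from the time the informed consent form is signed through 30 days (+7) after the day of the procedure". Under protocol 10.1.1, "A screening visit will be performed within 30 days prior to the scheduled procedure", although that visit may be combined with the surgery visit.

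Elsewhere the SAP does write a lower limit. In SAP 7.9.3.1, the readmission event must be one "with a start date of or after the index procedure date", and overall survival counts events from the procedure date.

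**The concern.** Section 7.9.2.2 is where the endpoint becomes a programming rule. Read alone, its window reaches back to the first recorded adverse event, which may fall up to about 30 days before surgery. Suppose a subject needs an intervention for the underlying disease in that interval, has it recorded as an adverse event, and then goes on to incision. If the event is adjudicated as related to the underlying disease, it meets every condition written there, although the device had not been used.

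The primary safety numerator would then differ from the protocol endpoint. Protocol 14.1 makes study success depend on the primary safety endpoint, and the cohorts are small enough that one subject can decide a test. If the gap is noticed only after data are seen, the choice of window becomes a post hoc dispute. Independent double programming (SAP section 8, Level I) would not catch it if both programmers code from 7.9.2.2.

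**Working it through.** **1. The passages side by side**

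| Place | Start | End |
|---|---|---|
| Protocol 14.4.2 | first incision | 30 days post-procedure |
| SAP 4.1.2 and 7.9.2 | first incision | 30 days post-procedure |
| Protocol 10.6 (adverse events, FAS) | first incision | study exit |
| SAP 7.9.2.2 (derivation) | none written | 30 calendar days post-procedure |
| SAP 7.9.3.1, endpoints 1, 4, 8 | none written | 30 calendar days post-procedure |
| SAP 7.9.3.1, endpoint 7 (readmission) | index procedure date | 30 calendar days post-procedure |

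**2. The plan's own power figures**

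Inputs from protocol 14.4.2:
- Nephrectomy and prostatectomy: performance goal (PG) 0.20, n = 49 after attrition, assumed rate 0.029, stated power 95%.
- Cystectomy: PG 0.45, n = 27 after attrition, assumed rate 0.141, stated power 83%.
- One-sided alpha 0.008, that is 0.025/3.

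The test is exact binomial, lower tail. Take the largest c with P(X ≤ c | n, PG) ≤ alpha; power is P(X ≤ c | n, assumed rate).
- n = 49: c = 3, attained alpha 0.0067, power 0.947 (stated 95%).
- n = 27: c = 5, attained alpha 0.0038, power 0.829 (stated 83%).

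Both reproduce. Alpha of 0.008 and of 0.025/3 give the same c. Writing in the first-incision start changes neither figure.

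**3. Effect of one extra counted subject**

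SAP 7.5 sets Holm levels of 0.025/(3+1−i), which are 0.00833, 0.0125 and 0.025.

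| n, PG | Events | One-sided p | 0.00833 | 0.0125 | 0.025 |
|---|---|---|---|---|---|
| 49, 0.20 | 3 | 0.0067 | pass | pass | pass |
| 49, 0.20 | 4 | 0.0214 | fail | fail | pass |
| 27, 0.45 | 5 | 0.0038 | pass | pass | pass |
| 27, 0.45 | 6 | 0.01251 | fail | fail (narrowly) | pass |

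With no attrition the first-step margin is again one subject: at n = 55, 3 events pass and 4 fail (p = 0.00865); at n = 31, 6 pass and 7 fail (p = 0.00845).

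**4. How often a cohort sits on that boundary**

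At the planning rates, P(X = 3 | 49, 0.029) = 11.6% and P(X = 5 | 27, 0.141) = 15.9%. A reversal caused by one extra subject also needs a qualifying pre-incision event in a subject not already counted.

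**5. Illustrative loss of power**

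The documents give no pre-operative Grade III rate, so q below is an assumption: the proportion of subjects with a qualifying pre-incision event, independent of later events. The counted rate becomes 1 − (1 − p)(1 − q), with p the planning rate, and c is unchanged.

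| q | Power, n = 49 | Power, n = 27 |
|---|---|---|
| 0 | 94.7% | 82.9% |
| 0.5% | 91.6% | 81.1% |
| 1% | 87.9% | 79.2% |
| 2% | 78.8% | 75.3% |
| 5% | 46.7% | 62.3% |

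The upper rows are the plausible ones; the lower rows only show the slope.

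**The case against.** The strongest reply is that the SAP does fix the start. Section 7.9.2.2 sits under 7.9.2, which names first incision; 4.1.2 and the protocol agree, and protocol 10.6 covers adverse event analysis in the FAS. The looser wording also has an ordinary explanation. Intraoperative events precede a post-procedure period, so the derivation needs some phrase to include them. In addition, Clavien-Dindo grades surgical complications, pre-existing conditions that have not worsened are not adverse events, and consent may fall on the day of surgery. All of this stands. It makes exclusion of pre-incision events the better reading of the plan as a whole.

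It does not remove the gap. The general definition and the operational rule differ, and neither document says which prevails. SAP version 3.0 revised this particular window, and the current text still has no start.

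A reader might infer from the readmission derivation that the omission is deliberate. The documents do not support that. Readmission is listed only as through 30 days, so its derivation has to supply a start, whereas the complication endpoints already carry one in their definitions. The contrast shows uneven drafting, not intent. It has somewhat more force for transfusion and reoperation (endpoints 4 and 8), for which the SAP states no start anywhere, but those endpoints are descriptive.

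**Conclusion.** The inconsistency is real and should be corrected before the database is locked. It lies within the SAP, between the definition in 4.1.2 and 7.9.2 and the derivation in 7.9.2.2. A reader might conclude that pre-operative events will count in the primary safety endpoint. That goes too far: they would count only if 7.9.2.2 were coded literally and in isolation.

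The consequence is limited. A wrongly included event makes the performance goal harder to meet, so the error runs against the device, costs power and cannot inflate type I error. No stated power changes. A single extra subject alters a cohort's result only at the boundary count, and at n = 49 or n = 27 only at the first two Holm steps. How often this might arise depends on a pre-operative event rate that the documents do not give. It is probably low, given the short or absent pre-operative interval and the need for a related Grade III event in a subject who still reaches incision.

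**What to change.** In SAP 7.9.2.2, replace the open window with: adverse event onset on or after first incision and on or before calendar day 30 post-procedure.

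Add a rule for events that start on the procedure date, because the listed inputs are dates and cannot place such an event before or after incision. One workable rule is to count them unless the record shows onset before incision.

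Apply the same lower limit to secondary endpoints 1, 4 and 8 in SAP 7.9.3.1.

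The cost is one phrase and one same-day rule in the SAP, plus a date condition in the program. No change is needed to the sample size, the performance goals or the multiplicity procedure.

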7.9.2.3 Performance Requirements

The null hypothesis will be rejected if the p-value for the one-sided hypothesis test is less than the multiplicity-adjusted alpha as described in **Section 7.5**. The performance goal for each indication is as follows:

Nephrectomy: 20%

Prostatectomy: 20%

Cystectomy: 45%

7.9.2.4 Rational for Performance Criteria

The literature search was performed based on available literature for each of the three surgery types (nephrectomy, prostatectomy, cystectomy). Point estimates along with 95% and 99% predicted intervals were calculated to provide plausible range of potential effect sizes. Clinically meaningful margins and statistical precisions have been considered to determine the appropriate performance goals. In some situations, considerations were also given to align with the studies from comparable sample sizes.

The full text detailing the performance goal rationales and justification for each is shown in the IDE CIP, Section 14.4.2.

7.9.2.5 Analysis Methods

The proportion of subjects experiencing a major complication will be calculated, with a one-sided 97.5% confidence upper bound. This proportion will be tested against the performance goals in **Section 7.9.2.3** using a Clopper-Pearson binomial exact test. The null hypothesis will be rejected if one-sided p-value is significant comparing to an alpha determined after multiplicity adjustments described in **Section 7.5** (Holm's method, i.e. Holm-Bonferroni method)¹.

7.9.2.6 Determination of Subjects/Data for Analysis

Subjects from the FAS will be included in this analysis.

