Nephrectomy	20%	55	The mean effect size is 0.029 with a 95% confidence interval of 0.022 to 0.038. The 95% prediction interval is 0.017 to 0.047. The 99% prediction interval is 0.014 to 0.058. A performance goal of 0.20, while greater than the predicted interval, broadly aligns with the upper limits for each nephrectomy study with a comparable study size (95% upper limits ranging from 0.100 to 0.539) and is clinically appropriate. A performance goal of 0.20, assuming a sample size of up to 55 (with 10% attrition n=49), one-sided alpha of 0.008 (Bonferroni Correction), and mean effect size of 0.029, results in a power of 95%.
Prostatectomy	20%	55	The mean effect size is 0.029 with a 95% confidence interval of 0.016 to 0.051. The 95% prediction interval is 0.004 to 0.173. The 99% prediction interval is 0.002 to 0.316. A performance goal of 0.20 (20%), is clinically appropriate. A performance goal of 0.20, assuming a sample size of up to 55 (with 10% attrition n=49), one-sided alpha of 0.008 (Bonferroni Correction), and mean effect size of 0.029, results in a power of 95%.
Cystectomy	45%	31	The mean effect size is 0.162 with a 95% confidence interval of 0.132 to 0.198. The 95% prediction interval is 0.047 to 0.354. The 99% prediction interval is 0.024 to 0.520. A performance goal of 0.45 (45%), is clinically appropriate. A mean effect size of 14.1% is used in the sample size calculations as it is more aligned with internal assumptions of the performance of Hugo. A performance goal of 0.45, assuming a sample size of up to 31 (with 10% attrition n=27), one-sided alpha of 0.008 (Bonferroni Correction), and mean effect size of 0.141, results in a power of 83%.

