7.1.3 Analysis Sets

The following populations will be considered for the analysis of data for this study:

Full Analysis Set

The full analysis set (FAS) is defined using the modified intent-to-treat (mITT) principle as all enrolled subjects for whom a Hugo™ RAS procedure was begun, with the beginning of a procedure defined as the first skin incision being made. In the event that a subject is consented, but the first incision does not occur (e.g., if the subject becomes ineligible during the timeframe between consent and the procedure day), that subject will not be considered part of the FAS. The FAS will be the primary analysis set for the evaluation of the primary and secondary endpoints.

Adverse Events (AEs) will be collected from the time of consent. AEs occurring in patients excluded from the FAS will be followed for 30 days post-consent through study exit and will be reported in a listing in the CSR. These AEs will not be included in the primary FAS analysis for either AE reporting or the analysis of the primary and secondary endpoints. The number and proportion of subjects experiencing each type of AE will be summarized by site, surgery type and overall for the FAS.

Per Protocol Analysis Set

The per protocol analysis set (PPAS) is a subset of the FAS including only those subjects without any major protocol deviations. Major deviation reasons are: "Enrolled subject did not meet enrollment criteria" and

“Unauthorized use of investigational device.” Reasons for exclusion of subjects from PPAS will be documented in tabular format and reported.

All enrolled subjects will be included in a subject disposition table indicating reasons for exclusion from the FAS and PPAS analysis sets.

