7.9.1.6 Determination of Subjects/Data for Analysis

The analysis of the primary effectiveness will be based on the FAS but following the mITT principle for the conversion endpoint by excluding any subject with that endpoint missing.

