7.9.3.6 Determination of Subjects/Data for Analysis

Subjects from the FAS with data available will be included for each secondary analysis. Secondary endpoint 2 will add the additional requirement that it will be for subjects who did not undergo conversion.

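### The primary safety analysis has no rule for subjects who exit before day 30; programmed as written, it counts them as complication-free unless a qualifying event was recorded first

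*SAP*

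**What the plan says.** **Population.** The full analysis set (FAS) is "all enrolled subjects for whom a Hugo™ RAS procedure was begun" (SAP 7.1.3), with first skin incision marking the start. Nothing about follow-up enters. For primary safety, SAP 7.9.2.6 reads in full: "Subjects from the FAS will be included in this analysis".

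**Derivation.** The rate "is calculated as the proportion of subjects who experience an AE with Grade III Clavien-Dindo classification or higher" that is related to device, procedure or underlying condition, up to 30 calendar days after surgery (SAP 7.9.2.2). The fields used are "The procedure date, AE start date, CEC-adjudicated relatedness" and the Clavien-Dindo grade. No visit date, exit date or last-contact date is used.

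**Other endpoints.** Effectiveness is analysed by "excluding any subject with that endpoint missing" (SAP 7.9.1.6). For secondary endpoints, "Subjects from the FAS with data available will be included for each secondary analysis" (SAP 7.9.3.6).

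**Missing data.** The primary analysis imputes nothing (SAP 7.4, Protocol 14.11). Multiple imputation is a sensitivity analysis if more than 5% of safety outcomes are missing (SAP 7.9.2.7). The tipping-point analysis is limited to effectiveness (SAP 7.12).

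**Exits.** Data up to exit are used and none are collected afterwards (Protocol 10.9.1). Early exits are not replaced (Protocol 10.9).

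**Sample size.** Power is computed after removing attrition. For cystectomy the text reads "assuming a sample size of up to 31 (with 10% attrition n=27" (Protocol 14.4.2). For nephrectomy and prostatectomy, 55 becomes 49.

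**The concern.** Surgical success is known on the day of surgery, yet its section says what to do when it is missing. The safety endpoint needs 30 days of observation, and its section does not. A programmer who follows 7.9.2.6 and 7.9.2.2 will put a subject lost on day 5 in the denominator and, finding no qualifying record, leave that subject out of the numerator. Independent double programming from the same text could reproduce the result without exposing the choice.

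Scoring a silent exit as event-free is an implicit imputation, which SAP 7.4 rules out. It also means that an early exit never registers as missing, so early exits could never set off the 5% trigger in 7.9.2.7. Each such exit enlarges the denominator without adding to the numerator, so the error runs one way, towards meeting the goal. Study success requires the safety endpoint to be met (Protocol 14.1).

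**Working it through.** **Inputs.** Performance goals (PG) are 20% for nephrectomy and prostatectomy and 45% for cystectomy (SAP 7.9.2.3). Expected rates are 0.029 and 0.141, and n is 55 reduced to 49 and 31 reduced to 27 (SAP section 6, Protocol 14.4.2). Holm levels are 0.025/3 = 0.0083, 0.025/2 = 0.0125 and 0.025 (SAP 7.5). The test is the exact one-sided binomial.

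**Formulas.** The pass mark c(n) is the largest x with P(Bin(n, PG) ≤ x) ≤ α. Power is P(Bin(n, p1) ≤ c(n)).

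**Step 1: reproduce the stated power (α = 0.008).**

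| Cohort | n | Pass mark | Power | Stated |
|---|---|---|---|---|
| Nephrectomy, prostatectomy | 49 | 3 | 94.7% | 95% |
| Cystectomy | 27 | 5 | 82.9% | 83% |
| Nephrectomy, prostatectomy | 55 | 3 | 92.5% | – |
| Cystectomy | 31 | 6 | 86.3% | – |

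The stated figures come back only with attrited subjects outside the analysis.

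**Step 2: pass marks under the two readings.**

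| Cohort | Denominator | 0.0083 | 0.0125 | 0.025 |
|---|---|---|---|---|
| Cystectomy | 31, exits kept in | 6 | 7 | 8 |
| Cystectomy | 27, exits left out | 5 | 5 | 6 |
| Nephrectomy, prostatectomy | 55, exits kept in | 3 | 4 | 5 |
| Nephrectomy, prostatectomy | 49, exits left out | 3 | 3 | 4 |

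For example, six cystectomy events give p = P(Bin(31, 0.45) ≤ 6) = 0.0027 with exits kept in, and P(Bin(27, 0.45) ≤ 6) = 0.0125 with exits left out. At 0.0083 the first passes and the second fails.

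**Step 3: true rejection probability at the goal.** Let e of N subjects exit, and let a fraction f of their events be recorded before exit. The observed count is Bin(N − e, PG) + Bin(e, f × PG), and rejection occurs if it is at most c(N). The 10% case has e = 31 − 27 = 4 and e = 55 − 49 = 6.

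| Cohort | Exits | f | 0.0083 | 0.0125 | 0.025 |
|---|---|---|---|---|---|
| Cystectomy | 4 of 31 | 0 | 1.3% | 3.4% | 7.7% |
| Cystectomy | 4 of 31 | 0.5 | 0.6% | 1.8% | 4.5% |
| Cystectomy | 4 of 31 | 0.75 | 0.4% | 1.3% | 3.2% |
| Cystectomy | 1 of 31 | 0 | 0.4% | 1.2% | 3.1% |
| Nephrectomy, prostatectomy | 6 of 55 | 0 | 0.7% | 2.1% | 5.5% |
| Nephrectomy, prostatectomy | 6 of 55 | 0.5 | 0.4% | 1.4% | 3.7% |
| Nephrectomy, prostatectomy | 6 of 55 | 0.75 | 0.3% | 1.1% | 3.0% |
| Nephrectomy, prostatectomy | 1 of 55 | 0 | 0.3% | 1.0% | 2.8% |

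For the 20% goals the first step never exceeds its level, because the pass mark is 3 at both sizes. A single exit exceeds the nominal level only at the 0.025 step.

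**The case against.** A reader might infer that the SAP prescribes scoring early exits as complication-free. The documents do not support that. No section says so, and SAP 7.4, SAP 7.9.2.7 and Protocol 14.11 all provide for missing safety outcomes. Read with 7.4, section 7.9.2.6 could mean FAS subjects with a known outcome. Nor is it right that safety data could never be missing in any sense, since a grade or relatedness rating can be absent from an event record. These points stand. They leave the term undefined for this endpoint, with the only explicit derivation giving the device-favouring answer.

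The contrast with secondary endpoints is limited. Several of them also come from adverse event records, and having data available is equally undefined there. The firm contrast is with effectiveness.

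The 10% is weak evidence of 30-day loss. The same allowance reduces 141 to 126 for effectiveness, which is settled at surgery. The protocol also works against silent loss: events are collected in surgery and through discharge, the day-30 contact may be by phone or video in extreme circumstances, three calls and a letter precede a lost-to-follow-up label, and modified data collection is preferred to exit. The f = 0 rows are therefore upper-end values.

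SAP 7.12 argues that missing safety data are unlikely because the endpoint would require hospitalization. The Grade III definition requires an intervention, and IIIa is one without general anesthesia; hospitalization is not part of it. In any case, an event after exit is not collected.

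**Conclusion.** The concern holds as a gap between sections. Applied literally, the population and derivation rules count a silent early exit as a non-event. That conflicts with the no-imputation rule, disables the 5% trigger for such exits, and departs from the basis of the power figures. No safety tipping-point analysis would reveal the effect. What the documents support is that missing is undefined and the literal program favours the device. They do not show that the sponsor intended this scoring.

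The size depends on two quantities that the plan does not give: how many subjects exit before day 30, and how many of their events are seen first. At 10% loss, the cystectomy error at the last Holm step is 7.7% with none seen and 4.5% with half seen, against 2.5%; for the 20% goals it is 5.5% and 3.7%. These figures assume a true rate equal to the goal and exits unrelated to outcome. The last step is reached only after the other two nulls are rejected. With one exit the error there is 3.1% (cystectomy) or 2.8% (20% goals), a small effect.

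**What to change.** In SAP 7.9.2.6 and Protocol 14.11:

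- Define a subject as evaluable for primary safety if they had a qualifying Grade III or higher event, or have adverse event status documented through day 30.
- Treat FAS subjects who exit earlier without such an event as missing, and leave them out of the primary denominator.
- Apply the 5% trigger to this definition. Say whether it works per surgery type or overall, and reconcile greater than 5% (SAP 7.4) with 5% or more (SAP 7.12).
- Report these exits by surgery type, with day and reason. Discontinuation reasons are already planned by center and by subject.
- Add a tipping-point or worst-case sensitivity analysis for safety, and amend SAP 7.12 to match.

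The cost is SAP and protocol wording, one evaluability flag and one extra sensitivity table. The downside should be stated: the denominator is slightly smaller and the rate leans mildly upward, because exits with an observed event stay in while event-free exits drop out. With a true rate of 45%, 4 of 31 exits and half their events seen, the expected rate is about (27 × 0.45 + 4 × 0.225) / (27 + 4 × 0.225) = 13.05 / 27.9 = 46.8%. That is conservative for a safety goal.
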